Cover Page for NCT02370251

Compassionate Use of Omegaven in Children

PI: [name]

February 19, 2018

COMPASSIONATE USE PROTOCOL
Compassionate Use of Omegaven for the Treatment of
Parenteral-Nutrition-Associated Liver Disease in Children
(IRB 5451)

Principal Investigator: [name], MSMI; Pediatrics, Neonatology
Sub-Investigators: [name]; Pediatrics, Gastroenterology
Safety Monitor: [name], MS, APRN; Clinical Nurse Specialist
Inpatient Study Nurses: [name]; Neonatology
 [name]; Neonatology
Outpatient Study Nurse: [name]; Gastroenterology
Data Manager: [name]; Neonatology
Regulatory Research: [name], APRN; Neonatology

Abstract

This is a single-group assignment, open-label protocol for the compassionate use of Omegaven® 10% in 200 children less than 6 years of age who are diagnosed with parenteral-nutrition-associated liver disease and have failed conventional lipid reduction strategies. The primary objective is to safely provide Omegaven (fish oil lipid emulsion) to Oklahoma children who are dependent on parenteral nutrition and to determine the number of these children who have resolution of their cholestasis while on the emulsion. Omegaven at the FDA maximum dose of 1 g/kg/day will be used with informed consent after the failure of conventional therapies to prevent the progression of liver disease. Children will be eligible if they are dependent on parenteral nutrition and have a direct bilirubin level of ≥ 2 mg/dL on two consecutive tests at least 48 hours apart while on an average of < 2 g/kg/day of parenteral lipids or ≥ 5 mg/dL on an average of 1 g/kg/day for 7 days prior. Lab studies will be obtained to monitor safety and efficacy. Children will remain on Omegaven until their physician or guardian decides to no longer utilize the lipid emulsion. Safety outcomes and the resolution of cholestasis will be monitored and reported to the FDA and IRB.

Background and Significance

Humans cannot synthesize the precursors of ω -3 (α -linolenic acid) or ω -6 (linoleic acid) fatty acids and must obtain them from their diet. In children who cannot tolerate full enteral feeds, the standard of care is to provide parenteral nutrition including IV lipids (fats). The most commonly used IV product, introduced in 1961, is Intralipid 20%, a soybean oil-based lipid emulsion rich in omega-6 fatty acids (ω -6). Omegaven 10% (Fresenius Kabi, Germany) was introduced in Europe in 2005. Fish oil is rich in very long chain ω -3 fatty acids, especially eicosapentaenoic acid (EPA) and docosahexaenoic acid (DHA), two conditionally-essential nutrients that have low rates of conversion from their precursor, α -linolenic acid.^{1,2,3}

Lipid emulsions consisting primarily of omega-6 fatty acids have been linked to the development of liver damage when used for a prolonged length of time as an excess of omega-6 has been found to be pro-inflammatory.^{1,2,3} Multiple studies have shown Omegaven useful for normalizing high direct bilirubin levels in comparison with Intralipid, as omega-3 is believed to attenuate the inflammatory response.^{1,2,3,4,5} Unfortunately, those receiving Omegaven as a *rescue therapy* after receiving a course of Intralipid have histologic liver specimens with decreased inflammation⁶ but still demonstrate steatosis (fatty liver) and cirrhosis of the liver.⁷ In a 2012 study by Puder,⁸ five groups of mice received different commercially-available lipid emulsions, including Intralipid and Omegaven. The only group to complete the study with normal liver histology had received Omegaven.

A retrospective cohort study that compared ω -3 to ω -6 lipid emulsions in 39 infants showed that it took 9.4 weeks in the ω -3 group versus 44.1 weeks in the ω -6 group to reverse cholestasis. Those in the ω -3 group also had lower mortality and liver transplant rates.⁹ Infants who started an ω -3 lipid emulsion with an initial direct bilirubin of <5 mg/dL had a lower mortality rate (6%) versus those who started the therapy with a direct bilirubin of >10 mg/dL (35%).⁴

One conventional therapy to prevent or treat cholestasis is lipid minimization, such that the IV lipid dose is reduced to levels below recommended intake amounts, compounding the growth failure inherent in infants with gastrointestinal disorders. In those receiving Omegaven, their dose is limited by regulations to 1 g/kg/day, also below the recommended lipid intake. Since fats have the highest caloric density of nutrients, maximizing intake is an important aspect of providing nutritional support. The combination of maximum Omegaven dosing supplemented with lower doses of Intralipid could theoretically provide a more balanced intake of essential fatty acids as well as improved growth in this vulnerable population.

Infants in our institution with severe PNALD were transferred outside of Oklahoma to centers approved to provide Omegave through “compassionate use” protocols as it is not available in the U.S. for routine use. In 2014, The Children’s Hospital had approximately 130 inpatient and 30 outpatient children between birth and 18 years of age with direct bilirubin levels above 4 mg/dL.¹⁰ Liver failure leads to approximately five liver transplants annually in Oklahoma children. While not all of these are due to parenteral nutrition, the ability to prevent even one transplant yearly would result in a massive savings of healthcare dollars as well as improved quality of life for those affected.

This protocol will help delineate the safety and efficacy of Omegaven for use in the treatment of PNALD in children less than 6 years of age. It has the potential to prevent or delay the need for liver transplantation in children who are exposed to long courses of intravenous nutrition while awaiting intestinal adaptation and growth and may provide a better alternative to our current sole use of ω -6 lipid emulsions associated with PNALD in children unable to achieve full enteral nutrition. It will also demonstrate the essential fatty acid profiles of infants receiving Intralipid (ω -6) as a sole source versus Omegaven (ω -3) as a sole source versus the combination.

PRIMARY OBJECTIVES:

To safely provide Omegaven on a compassionate use basis to Oklahoma children who are dependent on parenteral nutrition and have failed conventional lipid reduction strategies.

To determine the number of these patients who have resolution of their cholestasis (direct bilirubin < 2 mg/dL) within 60 days of initiation of the emulsion.

SECONDARY OBJECTIVE:

[figure not shown]
To determine if the essential fatty acid profile differs between those receiving only Intralipid, only Omegaven, or a combination.

To determine if infants who receive Omegaven have different developmental outcomes than those on Intralipid.

[figure not shown]
Lipid Emulsion Contents⁸

	Intralipid (ω-6)	Omegaven (ω-3)
Fat content (per 10 ml)	2 grams	1 gram
α-Tocopherol (vit E)	38 mg/L	150-296 mg/L
Phytosterols	348 mg/L	0 mg/L
Linoleic acid (ω-6 precursor)	50 g/L	1-7 g/L
Arachidonic acid (ω-6)	0 g/L	1-4 g/L
α-Linolenic acid (ω-3 precursor)	9 g/L	<2 g/L
Eicosapentaenoic acid (EPA; ω-3)	0 g/L	13-28 g/L
Docosahexaenoic acid (DHA; ω-3)	0 g/L	14-31 g/L

omega-6 fatty acids

omega-3 fatty acids

11

Preliminary Studies/Progress Report

[name], an associate professor at OU, has published several articles in the last 15 years specifically related to parenteral and enteral nutrition in extremely low birth weight infants. Her work is referenced in the 2009 “Nutritional Strategies for the Very Low Birthweight Infant.” She provides annual nutrition training to the clinical nursing team dedicated to the treatment of extremely low birth weight infants. As the Co-Chair of the NICU Nutritional Committee, she helped develop the first standardized parenteral nutrition solution started at OUMC NICU about 10 years ago. In 2015, she helped to develop off-the-shelf parenteral solutions for improved safety, efficiency, and cost in the NICU. She is the Leader of the NICU-GI Team, an interprofessional team providing comprehensive care to children with complex gastrointestinal disorders as they transition from the inpatient setting to home.

In the summer of 2016, the FDA approved a newer generation lipid emulsion, SMOFlipid which contains a mixture of soybean oil, coconut oil (MCT), olive oil, and fish oil.¹² Many places around the country have already switched to using this blend instead of the pure soybean product, especially for children whose cholestasis has resolved and are on home parenteral nutrition. Thus, at this time, clinical practice is likely to limit Omegaven use to a maximum of 3 years unless further evidence demonstrates it is superior to SMOFlipid.

In 2017, [name] published her findings in the Journal of Perinatology that 60% of infants on lipid minimization (~1 g/kg/day) with Intralipid (n=15) were found to have essential fatty acid deficiency while none of the infants on Omegaven (n=9) did. Furthermore, those who developed essential fatty acid deficiency (n=9) had a slower weight gain (19 g/kday) than those who did not (n=15) and gained 39 g/day.¹³

Research Design and Methods

Up to 200 children will be eligible for Omegaven use if they meet the following criteria:

- Live in or temporarily relocate to Oklahoma
- Age up to 6 years, both sexes, all races
- Have received at least 14 days of parenteral nutrition
- Have a direct bilirubin level of ≥ 2 mg/dL for two consecutive samples at least 48 hours apart and received parenteral lipids at a maximum dose of 28 g/kg over the two weeks prior OR have a direct bilirubin level of ≥ 5 mg/dL and received parenteral lipids at a maximum dose of 7 g/kg over the week prior

Exclusion criteria for enrollment:

- Known food allergy to fish
- Known metabolic disorder of lipid metabolism
- Active coagulopathies (active bleeding or requiring blood product treatment in the prior 48 hours)
- Medical condition likely to result in death in the next 30 days

Baseline labs (Table 1) will be obtained within 48 hours prior to starting Omegaven. An essential fatty acid profile will demonstrate the baseline profile on Intralipid. An Omegaven infusion will be started at a dose of 1 g/kg/day after informed consent is obtained. This is the maximum dose allowed by the FDA. Monitoring studies will be obtained per Table 1. Dosing modifications will be based on the parameters found on page 7 of the protocol. After the first month of Omegaven therapy, routine study labs will be obtained as well as an essential fatty acid profile which will demonstrate the profile on Omegaven.

Once the child's direct bilirubin level has normalized (below 2 mg/dL) and they have received at least four weeks of Omegaven, additional parenteral lipids may be added or adjusted at the discretion of the physician.

Enrolled children will have full growth assessments (weight, length, FOC) and nutritional assessments at every patient encounter (typically this is daily in the hospital and at every GI clinic visit). Any surgical procedures, medications, hospital readmissions, and/or infections directly related to the use of parenteral nutrition will be documented as well as any laboratory, radiology, or pathology data obtained for this purpose while the patient is receiving Omegaven or within 30 days of stopping the lipid.

Table 1: Laboratory Monitoring

	Baseline Day 0	Weekly	Every 2 Weeks	Monthly	After Last Omegaven Dose ¹
While DB \geq 2 mg/dL					
Direct bili	Day -1 to 0	\pm 3 days			Continue weekly until normal
CBC/diff	\pm 3 days		\pm 3 days		Within 7 days
AST/ALT/GGT	\pm 3 days		\pm 3 days		Within 7 days
Triglycerides Lipid panel	\pm 3 days			\pm 3 days	
PT/INR	\pm 3 days			\pm 3 days	Within 14 days
EFAP	Day 0		\pm 3 days		Within 30 \pm 7 days
When DB < 2 mg/dL					
Direct bili			\pm 3 days		
CBC/diff			\pm 3 days		Within 14 days
AST/ALT/GGT			\pm 3 days		Within 14 days
Triglycerides Lipid panel				\pm 3 days	
PT/INR				\pm 3 days	Within 14 days
EFAP			\pm 3 days		Within 30 \pm 7 days

¹If DB remains \geq 2 mg/dL, monitoring will continue until child is off Omegaven for 4 months. When feasible, an EFAP will be obtained approximately 4 weeks after the parenteral nutrition use has ceased.

Dosing Modifications Based on Triglyceride Levels:

- If triglyceride level \leq 250 mg/dL, continue lipids at current dose.
- If triglyceride level $>$ 250 mg/dL, repeat specimen when off lipids for 4 hours. If repeat is \leq 250 mg/dL, continue at current dose. If repeat is $>$ 250 mg/dL, decrease dose by 25% and repeat within 24 hours.
- If triglyceride level $>$ 500, stop lipids immediately with repeat level within 24 hours. Restart lipids at the discretion of the physician.

Other Dosing Modifications:

- For children unable to tolerate Omegaven due to a suspected allergy or toxicity or due to active bleeding believed to be caused or worsened by the lipid emulsion, the infusion may be decreased or stopped at the discretion of the child's medical team with the reason documented.
- The attending physician may choose to decrease or stop lipids at their discretion for any reason if they determine continuing may be detrimental to the patient with

the reason documented.

- If, for any reason, the supply of Omegaven is interrupted, the infant will receive the standard of care at an equivalent dose until Omegaven is available.

Outpatient Administration:

Children receiving Omegaven at the time of discharge must be seen within the first month in the OU Children's GI Clinic as an outpatient once they are discharged from the hospital. Further outpatient visits should occur no less frequently than every 2 months while on Omegaven. Weight, length, and FOC will be obtained on all children less than 2 years of age; weight and height should be obtained on all children over the age of 2 years. At each outpatient visit, enteral and parenteral nutrition volumes should be recorded. Any surgical procedures, medications, hospital readmissions, and/or infections directly related to the use of parenteral nutrition should be documented as well as any laboratory, radiology, or pathology data obtained for this purpose. Monitoring labs will be performed as per Table 1 as long as the child remains on Omegaven.

Children will be observed in the inpatient setting for a minimum of 48 hours after the initiation of Omegaven. Children will be eligible for Omegaven administration for up to 3 years. Two months before eligibility is lost via this IND, an individual IND will be submitted by the child's physician to the FDA if they expect that the child will need to require ongoing therapy. This can be completed via a new process as of January 2017 at: <http://www.fda.gov/downloads/Drugs/DevelopmentApprovalProcess/HowDrugsareDevelopedandApproved/ApprovalApplications/InvestigationalNewDrugINDApplication/UCM490130.pdf>

Option Care will be the outpatient provider for parenteral nutrition. They are familiar with the procurement and use of Omegaven and have procedures in place for providing training to the families before hospital discharge regarding the administration of parenteral nutrition as well as the reporting of potential adverse events. At the time of discharge, interested parties will be given information regarding potential AEs to be reported and how to directly contact the safety monitor and/or [name]. The family, home health nurse, primary care physician, and GI physician will report any suspected AEs to [name] and/or [name] (safety monitor).

Data Collection:

The following data may be collected for protocol adherence and patient safety analysis.

- Name
- Medical record number
- Date of birth
- Dates of hospitalization and/or outpatient visits
- Nutritional data (enteral and parenteral)
- Growth data (weight, length/height, FOC)
- Laboratory, microbiology, and pathology data
- Medications, including Ursodiol, phenobarbital, and other enteral lipid products
- Liver and/or intestinal transplant and other pertinent surgical procedures
- Neurodevelopmental testing results
- Mortality
- Adverse event data

Termination and Completion

Termination of a patient's participation will occur if the child develops a serious adverse event definitely caused by the lipid emulsion, if the child is diagnosed after enrollment with a fish allergy or a disorder of lipid metabolism, if the child is unable to tolerate the emulsion, if the child dies, if the child's guardian decides to no longer participate, or if the attending physician feels it is in the child's best interest. In the event this occurs, the date of and reason for termination will be recorded.

Completion of the study occurs when any of the following are met: the child is no longer receiving parenteral nutrition and the direct bilirubin level is <2 mg/dL, the direct bilirubin is ≥ 2 mg/dL and it has been 4 months since the cessation of Omegaven, Omegaven has been used for 3 years, or the child reaches 6 years of age. This does not preclude the patient from receiving the medication, but the patient's current physician will need to apply for a treatment IND and assume monitoring of the patient.

Data and Safety Monitoring Plan

All observed or volunteered adverse events (AE) will be investigated for seriousness and causality within 48 hrs of investigator awareness. AEs will be reported from enrollment through 30 calendar days after the last administration of Omegaven. A serious adverse event (SAE) includes any untoward medical occurrence that results in death, is life-threatening, requires prolongation of existing hospitalization, or results in significant disability.

We will assess adverse events using the following scale (i.e. 3D):

0=No or mild complication

1=Moderate complication with no long-lasting effects

2=Severe, life-threatening, or disabling complication

3=Death

A=UNRELATED or UNLIKELY (clearly not related to the study or the relationship appears to be remote and other factors suggest an alternative etiology exists)

B=POSSIBLE (one or more factors suggest a possible relationship but other etiologies seem equally or more likely)

C=PROBABLE (relationship seems probable because of a clear temporal association with the interaction, lack of alternative explanations for the experience, or other factors)

D=DEFINITE (clearly related to the study procedure)

Per FDA requirements, any unexpected fatal or life-threatening suspected adverse reactions will be reported within 7 days after initial receipt of the information. Any serious, unexpected suspected adverse reactions, findings from other clinical, animal, or in-vitro studies that suggest significant human risk, and a clinically important increase in the rate of a serious suspected adverse reaction will be reported to the FDA and all investigators within 15 days after determining that the information qualifies for reporting. Annual progress reports will be reported to the FDA within 60 days of the anniversary date that the IND becomes active (March 21, 2015). All adverse events will be reported to the IRB and the FDA on an annual basis, at minimum, when the protocol goes through annual review.

The Principal Investigator will meet with a data safety monitor, [name], APRN (clinical nurse specialist), quarterly to review any AE that were observed or volunteered over the previous quarter.

IRB Information

1) Sources of research material

The EMR will be utilized for obtaining clinical data, study outcomes, and

- information necessary for adverse event reporting. Laboratory work will be done as part of routine care and FDA requirements for receiving the emulsion.
- 2) Recruitment and Consent
 - a. Consent will occur either in the hospital setting at the patient’s bedside or in the outpatient clinic in a private room.
 - b. The consent and HIPAA forms will be printed in English and Spanish. Spanish-speaking families will be consented using a Spanish-speaking interpreter provided by the hospital. Families speaking languages will be informed via a language-specific translator and will be asked to sign the English consent form.
 - c. Parents/guardians will be provided the study forms, including the consent, with ample time to review the materials.
 - d. Families who would like to participate will need to be transferred to The Children’s Hospital at OUMC where the formal consent process will occur. The study is listed on ClinicalTrials.gov where the public has access to information regarding the study. It is possible that hospital social media or television advertisement may include information about this study.
 - 3) Intravenous nutritional products carry the risk associated with parenteral administration, including line sepsis and extravasation. In previous published studies, there have been no additional identified risks of adverse events associated with the administration of fish oil-based lipid over soybean oil-based lipid.
 - 4) Data will be collected by the study personnel in a private and confidential manner using the password-protected EMR or on paper forms in the patient’s chart. Any data collected for analysis will be kept in a password-protected database (REDCap) or Excel file on a secure server or in the locked offices of the investigators.
 - 5) Children may have direct benefit from participating in this study because they have access to a nutritional treatment that is suggested to be beneficial in the treatment of PNALD without a higher risk of adverse effects than the standard treatment. There may also be decreased sepsis and other adverse outcomes associated with inflammatory processes as well as the possibility of enhanced visual and neurodevelopmental outcomes with the inclusion of DHA in Omegaven.
 - 6) Despite not being FDA-approved, Omegaven has been in use in the US for the last decade for “compassionate use” and is approved for use in other countries in Europe. Potential benefits include the possibility of preventing progressive liver damage associated with long-term ω -6-fatty acid lipid emulsions.
 - 7) Several studies have shown the efficacy of Omegaven in resolving cholestasis

without any serious side effects reported. Children in this study may benefit from receiving a medication that provides protection against developing liver damage that is associated with the current standard treatment. The patient's insurance will be billed for the lipid emulsion at reasonable cost of acquisition plus storage and dispensing costs and the hospital has agreed to pursue payment as they do for all other treatments, including the use of charity, etc.

Literature Cited

1. Calder PC. N-3 polyunsaturated fatty acids, inflammation, and inflammatory disease. *Am J Clin Nutr* 2006;83;1505S-19S.
2. Calder PC. Use of fish oil in parenteral nutrition: rationale and reality. *Proc Nutr Soc* 2006;65:264-77.

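### The primary resolution count closes at day 60, 5.8 days before the only time to reversal the protocol cites for fish oil, and leaves out later resolutions that the trial already records

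*Combined protocol and SAP*

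**What the plan says.** The Primary Objectives section asks for the number of children "who have resolution of their cholestasis (direct bilirubin < 2 mg/dL) within 60 days of initiation of the emulsion". The Abstract states the same aim without a time limit: "to determine the number of these children who have resolution of their cholestasis while on the emulsion".

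The protocol's only figures for time to resolution are in Background and Significance, where a retrospective cohort of 39 infants is reported: "it took 9.4 weeks in the ω -3 group versus 44.1 weeks in the ω -6 group to reverse cholestasis". The text does not say whether these are means or medians, gives no spread, and does not define reversal.

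Treatment and measurement both run well past day 60. Outpatient Administration says: "Children will be eligible for Omegaven administration for up to 3 years". Table 1 schedules direct bilirubin weekly while it is 2 mg/dL or above and every two weeks once it is below. Footnote 1 to Table 1 says that, for a child who remains at 2 mg/dL or above, "monitoring will continue until child is off Omegaven for 4 months". Termination and Completion repeats the 4-month rule.

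The design is single-group and open-label, with up to 200 children. The protocol states no target resolution rate, no hypothesis test and no reason for choosing 60 days.

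**The concern.** The trial wants to know how many children clear their cholestasis on Omegaven. The window that defines the primary count closes slightly before the one summary time the protocol offers for fish oil, and long before treatment or follow-up need end. A child whose direct bilirubin first falls below 2 mg/dL in week 10 would be measured, and would count under the Abstract's wording, but not under the Primary Objectives.

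Two things are at stake. The primary number may be well below the number of children who resolve while treated, and a reader could take it as the latter. Also, a single proportion at day 60 cannot be set beside 9.4 and 44.1 weeks, which are times. With no concurrent control, those are the only benchmarks of this kind in the protocol.

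Reconciling the Abstract with the Primary Objectives would not settle the matter by itself. If the 60-day wording prevails, the unexplained horizon remains.

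**Working it through.** **Inputs.** Window: 60 days (Primary Objectives). Cited times: 9.4 weeks on omega-3 and 44.1 weeks on omega-6 (Background and Significance). The plan has no sample-size or power calculation, so there is no calculation to reproduce.

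**Step 1: common units.** 9.4 × 7 = 65.8 days. 44.1 × 7 = 308.7 days. 60 / 7 = 8.57 weeks. The gap is 65.8 − 60 = 5.8 days, and 5.8 / 65.8 is about 9%.

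**Step 2: share resolved by day 60.** The documents give neither the type of summary nor the distribution, so both are assumptions here. T is the time to resolution, with no deaths, transplants or early stopping.

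- Exponential, 65.8 as median: 1 − 2^(−60/65.8) = 46.8%.
- Exponential, 65.8 as mean: 1 − exp(−60/65.8) = 59.8%. The median of that distribution is 65.8 × ln 2 = 45.6 days.
- Weibull with shape k, 65.8 as median: 1 − 2^(−(60/65.8)^k) = 45.3%, 43.8% and 40.9% for k = 1.5, 2 and 3.
- Weibull, 65.8 as mean: the scale is 65.8/Γ(1 + 1/k), which gives 52.6%, 48.0% and 41.7% for the same k.
- Lognormal with log-SD s, 65.8 as median: Φ(ln(60/65.8)/s) = 37.9%, 42.7%, 45.4% and 46.3% for s = 0.3, 0.5, 0.8 and 1.0.
- Lognormal, 65.8 as mean: Φ((ln(60/65.8) + s²/2)/s) = 43.7%, 52.6%, 61.2% and 65.8% for the same s.

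The full range is about 38% to 66% resolved by day 60, so about 34% to 62% unresolved. If 65.8 days is a median, the resolved share cannot exceed one half under any distribution. If it is a mean, it can.

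**Step 3: what the 5.8 days are worth.** Under the exponential, a 66-day window gives 50.1% (median) or 63.3% (mean). The gains are 50.1 − 46.8 = 3.3 points and 63.3 − 59.8 = 3.5 points. Moving the cut-off to day 66 would change little.

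**Step 4: what a longer horizon does.** Take 26 weeks (182 days) as an illustration; this horizon is not in the documents. The exponential is used again, with each cited time read as a median or as a mean.

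| | Day 60 | 26 weeks |
|---|---|---|
| Omega-3, 65.8 days | 46.8% or 59.8% | 85.3% or 93.7% |
| Omega-6, 308.7 days | 12.6% or 17.7% | 33.5% or 44.5% |

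The longer horizon captures many more resolutions. By the same method, it also captures more resolution of the kind seen on omega-6.

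**The case against.** The strongest reply is that a fixed early landmark is a legitimate endpoint. In a single-group study a short window limits how much resolution that would have happened anyway is credited to the drug, and Step 4 shows that this background grows with the horizon. No decision, target rate or test hangs on day 60, so no error rate is affected. The count states its own window, and the protocol nowhere calls a child unresolved at day 60 a failure. Later values are not lost, and the Abstract says that resolution will be monitored and reported. All of this stands. It is a reason to keep the 60-day count and not to let a longer horizon replace it.

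The reply also limits what the 9.4-week figure can carry. It comes from a small retrospective cohort, and the protocol quotes it as background without adopting it as the expected time for its own population. Children who enter near 2 mg/dL might resolve sooner.

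A reader might infer more than the documents support:

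- *That the typical child resolves after day 60.* This follows only if 9.4 weeks is a median. If it is the mean of an exponential distribution, most children (59.8%) resolve by day 60.
- *That a definite number of the 200 children would be misclassified.* Such a number needs full enrolment, a horizon chosen by the reader, and no deaths, transplants or stopping. The plan says only "Up to 200 children will be eligible for Omegaven use if they meet the following criteria", and its Background cites mortality of 6% and 35% in two baseline-bilirubin groups.
- *That children with high baseline bilirubin lose most from the cut-off.* This is plausible, but the documents report mortality by baseline bilirubin, not time to resolution.

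The reply does not supply a reason for 60 days, and it does not bring later resolutions into the primary result.

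**Conclusion.** The point holds as an inexpensive improvement to the primary objective, not as a flaw that invalidates the study. The window is 5.8 days shorter than the protocol's only cited time to reversal on fish oil, and the documents do not explain it. If children follow a course like the cited one, a substantial share, roughly 34% to 62%, would still be unresolved at day 60. Resolutions after that day would be recorded but left out of the primary count.

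That range rests on assumed distributions, on reading 9.4 weeks as either a mean or a median, and on the absence of competing events. It indicates scale and is not a forecast. The unit conversion and the mismatch between the primary horizon and the length of follow-up are certain. How much the primary count would fall short of eventual resolution is not. The 5.8 days matter little in themselves; the loss comes from having no estimate beyond the landmark.

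**What to change.** Keep the 60-day count, label it an early landmark, and give the reason for 60 days if there is one. Add to the primary objective the time to, and cumulative incidence of, first direct bilirubin below 2 mg/dL from the start of Omegaven over all scheduled follow-up. Specify that:

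- death and liver or intestinal transplant are competing events, so that a fall in bilirubin after transplant does not count as resolution;
- each child is otherwise censored at the end of that child's follow-up;
- the estimate is reported at 60 days and at one prespecified later time, for example 26 weeks;
- a child unresolved at day 60 is described as not yet resolved;
- without a control group, later resolution cannot all be credited to Omegaven.

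Align the Abstract with the revised objective.

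Censoring is needed because status at 26 weeks will not be known for every child. A child who stops Omegaven at week 4 and is followed for 4 months (about 17 weeks) is observed to about week 21.

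The cost is a short addition to the objectives and one extra analysis of bilirubin values already drawn under Table 1, with no new visits or draws. The downsides are that the longer-horizon figure comes later for late enrollees and contains more background resolution than the 60-day count.

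### The primary count runs to Day 60, but the last required bilirubin draw can fall anywhere on Days 53-60, so some late resolutions can go uncounted

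*Combined protocol and SAP*

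**What the plan says.** The second item under Primary Objectives counts children who reach "resolution of their cholestasis (direct bilirubin < 2 mg/dL) within 60 days of initiation of the emulsion". The Abstract states the same aim without the time limit: "to determine the number of these children who have resolution of their cholestasis while on the emulsion".

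The schedule is in "Table 1: Laboratory Monitoring". Its first column is "Baseline Day 0", followed by weekly, two-weekly, monthly and after-last-dose columns. Direct bilirubin is drawn at Day -1 to 0, then weekly ±3 days while it is at or above 2 mg/dL. After the last dose the entry is "Continue weekly until normal". No column or footnote sets a draw at Day 60.

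Outpatients follow the same table: "Monitoring labs will be performed as per Table 1 as long as the child remains on Omegaven". The documents have no rule for which draw closes the 60-day count, or for how a first value below 2 mg/dL seen on Days 61-66 is classified.

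**The concern.** Sixty is not a multiple of seven, so the cut-off falls between two scheduled draws. A child whose bilirubin first drops below 2 mg/dL after the last in-window draw, but by Day 60, meets the objective and yet has no required sample to show it.

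Take two children who both cross on Day 57. One is drawn on Day 54 and then Day 61; the other is drawn on Day 59. All these draws comply with Table 1, but only the second child is counted.

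At stake is the only efficacy count among the primary objectives. For a single lasting crossing, the error can only lower the count, and enrolling more children does not average it out. The Background cites a study in which "it took 9.4 weeks in the ω -3 group versus 44.1 weeks in the ω -6 group to reverse cholestasis". The first figure is about Day 66, close enough to the cut-off that crossings in the last week before Day 60 are plausible.

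**Working it through.** The plan gives no sample-size calculation, target rate or precision figure, so there is no stated number to reproduce. The check has two parts: the range of last draw days, which follows from Table 1, and the size of the loss, which needs assumptions.

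**1. Last required draw on or before Day 60**

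Inputs: Day 0 anchor, weekly draws, ±3 days (Table 1); 60-day limit (Primary Objectives).

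- Week 8: 56 ± 3 = Days 53-59.
- Week 9: 63 ± 3 = Days 60-66.
- The last in-window draw is the week-9 draw if it is taken on Day 60, and otherwise the week-8 draw. The range is therefore Days 53-60.
- With draws exactly on schedule it is Day 56.
- Table 1 implies but does not state that weeks are counted from Day 0. If ±3 days runs from the previous draw (gaps of 4-10 days), the range is Days 51-60.

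**2. Size of the loss**

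Inputs: 9.4 weeks × 7 = 65.8 days (Background); a maximum of 200 children (Research Design and Methods). Assumptions not in the documents: 65.8 days is a median, and time to resolution is Weibull with shape k = 1 or 2.

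F(t) = 1 − exp(−ln 2 × (t/65.8)^k). The loss for a last draw on day d is F(60) − F(d).

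| | k = 1 | k = 2 |
|---|---|---|
| F(60) | 46.8% | 43.8% |
| F(56) | 44.6% | 39.5% |
| F(53) | 42.8% | 36.2% |
| Loss, every last draw on Day 56 | 2.3 points | 4.3 points |
| Loss, every last draw on Day 53 | 4.1 points | 7.6 points |

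Average loss under two patterns of draw days:

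- *Week-8 and week-9 days independent and uniform over their windows.* The last draw is Day 60 with probability 1/7, and otherwise uniform on Days 53-59. The loss is 2.0 points (k = 1) to 3.7 points (k = 2). Times 200, that is 3.9 to 7.4 children.
- *Each child keeps one constant offset from −3 to +3 days, all equally likely.* The last draw is then one of Days 54-60. The loss is 1.7 to 3.2 points, or 3.4 to 6.5 children of 200.

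Upper bound (every child last drawn on Day 53): 200 × 0.041 = 8 to 200 × 0.076 = 15 children.

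Sensitivity: if 65.8 days is instead the mean of an exponential, F(60) = 59.8% and F(53) = 55.3%. The largest loss is 4.5 points and the average with independent uniform draws is 2.2 points, much the same as for k = 1.

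For scale, the 95% half-width for a proportion of 0.47 with n = 200 is 1.96 × √(0.47 × 0.53 / 200) = 6.9 points.

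**The case against.** The strongest reply is that this is ordinary interval censoring. The endpoint is cumulative, about eight weekly draws measure it, and any endpoint read from periodic laboratory tests has the same feature. The protocol is single-group compassionate use with no comparator, test or target rate, and the average shift is smaller than the sampling error at n = 200. That limits how much the point matters. It does not supply a closing observation.

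The objective is also not restricted to Table 1 samples. The protocol records laboratory data obtained while the child is on Omegaven and takes outcomes from the medical record, so a routine bilirubin on Days 54-60 would count. This stands in part: such draws narrow the gap, but the protocol does not require them.

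The size rests on one summary figure from a retrospective study of 39 infants, which the protocol does not identify as a mean or a median. The Weibull shapes are assumed, 200 is a ceiling ("Up to 200 children will be eligible for Omegaven use if they meet the following criteria"), and deaths and early stopping are ignored. All of this stands, so the figures are illustrative.

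A reader might infer more than the documents support:

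- *That the window itself closes on different days for different children.* It closes on Day 60 for all; what varies is the last day on which resolution must be looked for.
- *That outpatients, or children drawn early, are under-counted.* The same table applies to outpatients, and nothing says that they are drawn earlier. A child always drawn three days early is sampled on Day 53 and again on Day 60, and loses nothing.
- *That the net error must be downward.* This holds for a single lasting crossing. As worded, one unconfirmed value below 2 mg/dL is enough, so a transient dip could push the count up.

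**Conclusion.** The point holds as a minor mismatch between the 60-day objective and the laboratory schedule. Followed exactly as written, the plan can leave up to a week before Day 60 with no required bilirubin (Days 54-60 if the last draw was on Day 53). The Days 53-60 range needs only Table 1 and a Day 0 anchor.

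The average under-count of about 2-4 percentage points, roughly 3-7 children if all 200 enrol, also needs 9.4 weeks to be a median, Weibull shape 1 to 2, draw days spread evenly over their windows, and no help from routine samples. The 4-8 point figure is an upper bound on the Day 0 reading and should not be quoted as the expected loss.

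The point applies only to the wording under Primary Objectives. If the Abstract's wording governs, there is no Day 60 cut-off and the mismatch disappears. The protocol should therefore settle which one is meant.

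**What to change.** In Table 1, set the week-9 direct bilirubin at Day 60 for every child not yet below 2 mg/dL, inpatient or outpatient, and state that this value closes the primary count. Day 60 is already the first day of the week-9 window (Days 60-66), so no sample is added.

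The cost is one line of text. That draw loses its ±3-day flexibility, and it may closely follow a late week-8 draw (Day 59 and then Day 60 at the extreme).

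Running the count through the week-9 draw at Day 63 ±3 would not solve the problem. The closing observation would still vary over Days 60-66, and resolutions after Day 60 would be admitted, contrary to the objective.

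At the same time, reconcile the Abstract with the Primary Objectives so that both state the same time limit.
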